4.1.1 General Design Description

We will conduct a phase 1 clinical trial with two groups randomly assigned in parallel. The experimental group (PD-MI) will receive mental imagery training and the control group (PD-Con) will receive psychoeducation (see Figure 3).

Within two weeks of obtaining consent and completing initial phone and online video-screening, subjects will complete online surveys and arrive for an in-person visit to complete the screening process including the comprehensive evaluation of baseline cognitive functioning, performance-based tests, and neurological exam. At the end of this visit, eligible subjects will be randomized to two groups, PD-MI and PD-Con.

Within two weeks of Visit 1, subjects will return for Visit 2 to assess baseline imagery skills and perform fMRI tasks in the scanner. Subjects in the PD-MI group will be interviewed in Visit 2 to gather information about their daily activities and goals for imagery script development.

Following Visit 2, subjects will start their respective trainings for 6 weeks. The one-on-one training sessions will be delivered via videoconferencing.

We will guide the subjects in the PD-MI group using personalized scripts during one-on-one mental imagery training 3 times a week for the first 4 weeks. We will also record the mental imagery scripts (each 5-10 min) for self-practice on none-training days in the first 4 weeks and for daily homework in the subsequent 2-week block. After each daily practice in the 2-week block, subjects will be asked to submit a detailed mental imagery diary via the Yale REDCap online survey platform. Subjects will also be called once a week in the 2-week block for check-in.

[figure not shown]
The control group (PD-Con) will receive psychoeducation 3 times a week for 4 weeks regarding cognitive functioning and brain health in PD. Subjects will receive private video links with pre-recorded PowerPoint lectures covering topics such as basic brain anatomy, neuroplasticity, attention-executive function, memory, speech-communication, hallucinations and delusions, sleep, diet, physical activity, mood disorders, stress, and social bonds. On no-lecture days and in the subsequent 2-week block, subjects will receive online quizzes covering the lecture topics to be completed via Yale REDCap online survey platform. Subjects will also be called once a week in the 2-week block for check-in.

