4.3.2 Eligibility Criteria/Vulnerable Populations

In order to be eligible for inclusion in the study, an individual must meet all of the following criteria:

- Subjects with a diagnosis of idiopathic PD defined according to the International Parkinson and Movement Disorder Society (MDS) Clinical Diagnostic Criteria for PD⁷⁵
- Age \geq 40 years
- Expected to be on a stable dopaminergic medication regimen throughout the study period

Any individual who meets any of the following criteria will be excluded from participation in this study:

- Age < 40 years
- Non-English speaking
- Pregnancy
- Breastfeeding
- Excessive alcohol consumption (> 7 drinks per week for women, > 14 drinks per week for men) or illicit substance use
- History of a neurological disorder such as a brain tumor, stroke, central nervous system infection, multiple sclerosis, movement disorder (other than PD), or seizures
- History of schizophrenia, bipolar disorder, attention deficit disorder, or obsessive-compulsive disorder
- History of head injury with loss of consciousness longer than a few minutes
- Metallic surgical implants or traumatically implanted metallic foreign bodies
- Inability to lie flat for about an hour in the MRI scanner
- Discomfort being in small, enclosed spaces
- Dementia at screening (Video-Montreal Cognitive Assessment score < 21/30⁸⁰⁻⁸²)
- Cognitive problems in activities of daily living suggestive of more than mild cognitive impairment (PD Cognitive Functional Rating Scale > 4⁸³)
- Mild cognitive impairment according to the MDS Level II comprehensive assessment criteria (> 2 SD below the norm in two tests in a single cognitive domain or in one test in two separate cognitive domains). Note: The cutoff of 2 SD below the norm will apply to all domains including attention, verbal and visual memory, language, visuospatial skills, and executive functions.⁷⁶
- Hoehn & Yahr stage > 3 (i.e., able to stand and walk, but not fully independent⁸⁴)
- Focal neurological findings on exam that suggest cerebral pathology other than that associated with parkinsonism
- Motor symptoms that could potentially introduce too much motion artifact in the imaging data (e.g., MDS-Unified PD Rating Scale resting tremor score > 2 in limbs, head/chin tremor, or more than mild dyskinesia by history or exam⁸⁵)
- Failure to adhere to training and homework requirements (i.e., less than 75% adherence to one-on-one sessions and less than 50% homework completion rate)

- Failure to adhere to protocol

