Mental Imagery Training: Subjects in the PD-MI group will receive personalized training during one-on-one sessions 3 times a week for the first 4 weeks. Training will be offered via Zoom. Subjects will be guided to mentally simulate the planning and implementation of everyday tasks (e.g., going grocery shopping). The training sessions will last about 15-20 min. We will also record the mental imagery scripts for self-practice on no-training days in the first 4 weeks and for daily homework practice in the subsequent 2-week block. After practice, subjects will be asked to submit a detailed daily mental imagery diary via the Yale REDCap online survey platform. We will structure this diary based on the key elements of mental imagery including the setting of the activity, components of the activity, contextual cues, episodic details, emotional experiences, and vividness and difficulty level of the mental imagery exercise. Subjects will also be called once a week in the last 2 weeks for check-in.

Psychoeducation: Subjects in the PD-Con group will receive psychoeducation 3 times a week for 4 weeks regarding cognitive functioning and brain health in PD. Subjects will receive private video links with pre-recorded PowerPoint lectures covering topics such as basic brain anatomy, neuroplasticity, attention-executive function, memory, speech-communication, hallucinations and delusions, sleep, diet, physical activity, mood disorders, stress, and social bonds. The lectures will last about 15-20 min and will be accompanied by three multiple-choice questions to be completed via REDCap online survey platform to assess content comprehension. On no-lecture days in the first 4 weeks and in the subsequent 2-week block, subjects will receive quizzes covering the lecture topics to be completed via REDCap online survey platform. Subjects will also be called once a week in the last 2 weeks for check-in.

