In addition, the recruitment services at the YCCI including the YCCI clinical trials website and the YCCI social media support will be used to advertise the study. The same language in the study flyer will be used for advertisements. We will also utilize the YCCI recruitment database. YCCI has an ever growing “Help us Discover” database of more than 14,000 individuals who have expressed interest in clinical research at Yale. Emails are sent periodically to the group to maintain engagement and research interest. Researchers and study teams have found the communications have increased interest and clinical trial recruitment after each YCCI email campaign.

Lastly, we will also make use of the recruitment services offered by JDAT (EPIC/MyChart alerts & mailing) and Department/Center newsletters.

Enrollment

See Table 2. Planned Enrollment and explanations in Section 4.3.

Retention

We will ensure that the logistics of the study is straightforward in order to maximize subject compliance and retention. The Yale MRRC and YCCI are located in the Yale School of Medicine campus in close proximity to each other. No other research sites will be involved. We will email subjects the video link of a virtual tour of the MRRC and YCCI outpatient facility, so that they can familiarize themselves with the research sites (lobby, waiting area, behavioral testing rooms, scanner rooms, etc.) prior to their visit. Subjects will also be provided written directions and maps to the research site. Parking is always available in two garages near both research sites. Subjects who do not feel comfortable driving and have nobody else to drive them will be offered transportation. Subjects will be compensated for their participation and for travel expenses (e.g., parking, cab ride).

The one-on-one mental imagery training for the experimental group and psychoeducation for the control group will be administered via the Zoom video platform and private video links, respectively, eliminating the burden of in-person visits on the subjects. The video visits will be scheduled at convenient times for the subjects. Several surveys will also be administered online via the Yale REDCap survey platform, which will provide the subjects with enough time and flexibility to fill them out. All subjects will also submit their homework via REDCap, which will allow us to monitor compliance in a timely fashion.

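### Training non-adherence, which can arise only after randomisation, is listed as an exclusion criterion; its session limit can be applied only in PD-MI, and nothing says whether excluded subjects are followed or analysed as randomised.

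*Combined protocol and SAP*

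**What the plan says.** Section 4.3.2 introduces its exclusion list with "Any individual who meets any of the following criteria will be excluded from participation in this study". Near the end of that list stands "Failure to adhere to training and homework requirements (i.e., less than 75% adherence to one-on-one sessions and less than 50% homework completion rate", followed by an undefined item, "Failure to adhere to protocol".

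On timing, section 4.1.1 says of Visit 1: "At the end of this visit, eligible subjects will be randomized to two groups, PD-MI and PD-Con". Training starts only after Visit 2.

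On what each arm receives, section 5.3.2 separates "The one-on-one mental imagery training for the experimental group and psychoeducation for the control group": the first is given by videoconference, the second through private video links. Section 5.1 confirms this for PD-Con: "Subjects will receive private video links with pre-recorded PowerPoint lectures". Its homework is quizzes: "subjects will receive quizzes covering the lecture topics to be completed via REDCap online survey platform". Each lecture "will be accompanied by three multiple-choice questions to be completed via REDCap online survey platform to assess content comprehension", but no minimum is set for lectures viewed or for those questions.

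On follow-up and analysis:
- Sections 4.1.1 and 5.1 have all subjects returning for Visits 3 and 4, and section 4.2.1 has the outcomes collected from all subjects.
- Section 5.4.1 takes the subjects in the two groups as the units of observation.
- Section 5.4.6 uses complete cases when at most 5% of data are missing. Above that it uses multiple imputation, for the primary cognitive outcome only. Voxelwise imaging analyses are always limited to complete cases.
- Section 2.3.1 (Subject monitoring) ends participation for non-compliance with protocol evaluations and does not mention training.

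**The concern.** An exclusion criterion is normally settled before allocation. This one depends on behaviour during the assigned intervention, so it can act only after allocation, and the behaviour it measures differs between the arms. If applied as written, and if excluded subjects contribute no outcome data, each arm is reduced by a different filter. The subjects who remain are no longer the groups that randomisation formed.

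What is at stake is the between-group comparison for the primary outcomes. For Neuro-QoL, imputation might recover the loss, but section 5.4.6 does not name the imputation variables. For imaging, no method of recovery is planned. There is also discretion. The choice between the two readings of the adherence rule, and the judgement of who failed to adhere to the protocol, could be made after outcomes are known.

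**Working it through.** **1. Order of events.** Randomisation is at the end of Visit 1. Visit 2 follows within two weeks, and training follows Visit 2 (section 4.1.1). No subject can have a training or homework record before allocation, so the item cannot act as a screening criterion.

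**2. How the rule falls on each arm.** PD-MI has 3 sessions a week for 4 weeks, so 12 sessions; below 75% means fewer than 9. PD-Con has 12 lectures and no one-on-one sessions.

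| Subject | Both limits must fail (*and*) | Either limit is enough (*or*) |
|---|---|---|
| PD-MI, 8 of 12 sessions, 60% homework | stays | excluded |
| PD-MI, 12 of 12 sessions, 40% homework | stays | excluded |
| PD-Con, 0 of 12 lectures, 60% of quizzes | stays | stays |
| PD-Con, 12 of 12 lectures, 40% of quizzes | stays | excluded |

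Read as *and*, no PD-Con subject can meet the rule. Read as *or*, PD-Con is judged on homework alone.

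**3. The plan's own sample size.** The G*Power between-factors model has noncentrality λ = f²·N·m / (1 + (m − 1)ρ), with f = 0.266, m = 2 and df = (1, N − 2). The plan gives no ρ. With ρ = 0.5 assumed, N = 86 gives power 0.80, which reproduces section 5.4.2. Two 15% dropout steps, rounded up, give 102 and then 120.

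**4. Possible size of the bias (illustration only).** Assumptions not in the documents: no true effect; the lowest adherers are removed; correlation r between adherence and change is 0.2 to 0.5; SD of change is 7.25. Section 5.4.2 gives 7.25 as a cross-sectional SD; the two agree only at a within-subject correlation of 0.5.

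Complete-case bias = r × [k(p₁) − k(p₀)] × 7.25, where k(p) = φ(z_p)/(1 − p) and p₁, p₀ are the shares removed from PD-MI and PD-Con. Here k(0.15) = 0.2743, k(0.10) = 0.1950 and k(0) = 0.

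| Removed, PD-MI / PD-Con | r = 0.2 | r = 0.5 |
|---|---|---|
| 15% / 10% | 0.2 × 0.0793 × 7.25 = 0.11 | 0.5 × 0.0793 × 7.25 = 0.29 |
| 15% / 0% | 0.2 × 0.2743 × 7.25 = 0.40 | 0.5 × 0.2743 × 7.25 = 0.99 |
| 15% / 15% | 0 | 0 |

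**5. Does imputation remove it?** The planned 15% dropout by week 6 exceeds the 5% trigger, so imputation is the plan's route for Neuro-QoL. Suppose the model uses only group and baseline, and adherence is independent of baseline. Removed and retained subjects then have the same baseline distribution, so the imputed values follow the retained subjects and the bias stays. Simulation agrees: about 0.14 to 0.30 points (15% / 10%) and 0.42 to 0.99 points (15% / 0%). If adherence is related to baseline, baseline can recover part of the bias. With recorded adherence added to the model, the bias falls to within about 0.03 points of zero, given a linear relation and adherence recorded in both arms.

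**6. Cost of keeping everyone.** Suppose 15% of PD-MI gain nothing and are retained. The average difference becomes 4 × 0.85 = 3.4 points and f becomes 0.266 × 0.85 = 0.226. In the model of step 3:

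| N measured | Undiluted | 15% diluted |
|---|---|---|
| 120 | 0.92 | 0.81 |
| 102 (= 120 × 0.85) | 0.87 | 0.74 |

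**The case against.** The strongest reply is that the protocol already leans towards keeping everyone. All subjects are to return, outcomes are collected from all subjects, and the units of observation are the subjects in the two groups. The adherence item may be loose drafting, and dropout in the previous imagery study did not differ significantly by arm (section 5.3.2).

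Part of this stands. A reader might infer that the plan removes non-adherers from the analysis. The documents do not say so: section 4.3.2 does not define what exclusion entails. A reader might also infer that the protocol deliberately sets different limits by arm. It does not: it states one rule, and the inequality arises because one half of that rule has no counterpart in PD-Con.

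The rest does not settle the matter. None of the inclusive phrases mentions subjects who meet an exclusion criterion. Section 5.3.2 counted homework non-compliers as dropouts in the previous study. The similar dropout there is weak reassurance, because both of its arms practised imagery (section 1.2), whereas here the tasks differ and only one arm has sessions to miss.

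A further fair point concerns imaging. The complete-case sentence in section 5.4.6 refers to voxelwise analyses, while the primary imaging outcome is pairwise connectivity among 268 nodes (section 5.4.3). It presumably covers both, but that is an inference. Nor can an error rate for the imaging test be read from this illustration, since the planned test is FDR-corrected across node pairs.

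**Conclusion.** The concern holds as a gap in wording with consequences for the analysis. An event that can occur only after randomisation is listed as a ground for exclusion. Its session limit can be applied in one arm only. No section provides for follow-up or as-randomised analysis of those excluded. Confidence in this is high.

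The size is not established. A reader might infer that the result will be biased in favour of mental imagery. The documents support neither a direction nor a magnitude: they give no non-adherence rate for this trial and no relation between adherence and outcome, and equally selective loss gives no bias. On the assumptions in the working, the bias is 0.11 to 0.29 points for a modest imbalance. It reaches 0.40 to 0.99 points only if the full 15% forecast dropout falls in PD-MI, is all due to low adherence, and none falls in PD-Con. Against a 4-point target the modest case is small. The gap should be fixed because it is avoidable and cheap to close before outcomes are seen.

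**What to change.** 1. **Section 4.3.2.** Move the training and homework adherence item out of the exclusion list. State that non-adherence to training or homework does not by itself end follow-up, and that such subjects are still asked to attend Visits 3 and 4.
2. **Section 5.4.** State that all randomised subjects are analysed in their assigned group whatever their adherence. In section 5.4.6, make the complete-case restriction name the pairwise connectivity and graph analyses, and define it as subjects with usable scans at the timepoints the model needs, never selected on adherence.
3. **Section 5.4.6.** Include recorded adherence, by arm, in the Neuro-QoL imputation model.
4. **Supplementary analysis.** Use the 75% and 50% limits only there. Say whether either or both must fail, and give PD-Con a matching definition, such as lectures counted by completion of their three REDCap questions.
5. **Reconciliation.** Ask the sponsor to define failure to adhere to protocol, and to reconcile it and the adherence item with the termination conditions in section 2.3.1. Which stopping rule applies is for the sponsor to decide.

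The cost is protocol wording and outcome visits for a few subjects already within the 120. The adherence data are already planned: Zoom visit records (section 2.3.1), REDCap homework (section 5.3.2) and lecture questions (section 5.1). The real price is dilution, with power of 0.81 or 0.74 in the 15% case shown above. Excluding non-adherers would not recover that power for the same question. It would change the question to the effect among adherers, which randomisation does not protect.

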5.1 Study Procedures

All study procedures will be performed for research purposes.

Recruitment:

We will recruit individuals with PD directly through the Yale Movement Disorders outpatient clinics. The outpatient clinics in the new Yale PD Comprehensive Care Center will also be a source of recruitment. PD patients will be informed about the study during their visit at the clinics and provided with the study material. Interested patients will be contacted directly by the study team for initial screening.

We will also attend meetings at the local PD support groups and nonprofit organizations (e.g., American PD Association Connecticut Chapter, Beat PD Today exercise program) that provide educational and wellness programs for the greater PD community in Connecticut to present the proposed study to potential subjects.

Recruitment flyers will also be mailed to the providers at the neurology practices in Connecticut who care for patients with PD. Letters including study flyers will also be mailed to interested candidates.

In addition, the recruitment services at the YCCI will be used. Specifically, we will be utilizing the YCCI recruitment database. YCCI has an ever growing “Help us Discover” database of more than 14,000 individuals who have expressed interest in clinical research at Yale. Emails are sent periodically to the group to maintain engagement and research interest. Researchers and study teams have found the communications have increased interest and clinical trial recruitment after each YCCI email campaign.

We will also make use of the recruitment services offered by JDAT (EPIC/MyChart alerts & mailing) and Department/Center newsletters.

Consent

Verbal consent will be obtained for the screening visit over the phone or via email. Electronically signed informed consent will be obtained at the beginning of the video screening visit. A member of the research team authorized to obtain consent will give the subjects detailed information about the study and go over all aspects of the research. The purpose, research procedures, any risk that these procedures might entail, and any possible benefits will be discussed in detail in language appropriate for the individual's level of understanding. Subjects will be encouraged to ask questions and given enough time to discuss any aspect of the study with the research team. Subsequently, they will have to demonstrate understanding of the study procedures and what is expected of them. Once subjects understand the study, they will be asked if they wish to participate. If they do, they will be asked to electronically sign the consent form.

Capacity will be assessed directly in the course of attempting to obtain informed consent. When the member of the research team authorized to obtain consent has reviewed the study, they will ask the subject to explain the major elements of the study. Those elements are a) this is a research study (not routine treatment), b) participation is voluntary, c) study procedures, d) risks, e) benefits. Open-ended questions such as “Can you tell me the main things that you would do in this study? Can you tell me the main risks of the study?” will be

[figure not shown]
used to assess understanding and appreciation of the facts. Subject will then be expected to make a rational choice: "Considering the risks and benefits we have discussed, would you like to take part in this study?" Based on the subject's responses the team member will make a final judgment about capacity for consent. If the subject has capacity and agrees to the study, they will sign the consent form

Study Schedule

See also Figure 4 for study schedule and timeline.

Initial Screening: After obtaining verbal consent, subjects will complete an initial phone call screening for MRI safety and medical history. If the subject fails the MRI safety screening or meets any of the exclusion criteria for medical history, they will be excluded from the study. Subjects who are still eligible will be scheduled for a follow-up video-screening via the Zoom videoconferencing platform. Consent process will take place at the beginning of this visit. Subjects will electronically sign the consent form via REDCap. The screening will be for demographic data, global cognition, and functional abilities. We will administer the MoCA to assess global cognition.⁸⁰ We will use the PD Cognitive Functional Rating Scale for daily functional abilities.⁸³ If a subject scores below the eligibility criteria of our screening, they will be excluded from the study and their data will not be used.

Figure 4. Study Timeline.

Online Surveys: To evaluate the contribution of nonmotor factors to cognitive functioning, the Geriatric Depression Scale,⁸⁶ Parkinson Anxiety Scale,⁸⁷ Starkstein Apathy scale,⁸⁸ PD Quality of Life Questionnaire-39,⁸⁹ Parkinson Fatigue Scale,⁹⁰ and Scales for Outcomes in Parkinson's Disease – Sleep⁹¹ via the Yale REDCap online survey platform to those who pass the initial screening.

Visit 1: Baseline movement and cognitive evaluations to determine eligibility and baseline performance-based tasks: Visit 1 will be scheduled within two weeks after initial screening to complete the screening process. We will determine the disease severity with the MDS-Unified PD Rating Scale (MDS-UPDRS)⁸⁵ that also includes the Hoehn & Yahr staging.⁸³ We will administer the Wechsler Test of Adult Reading⁹² to determine premorbid IQ, and perform a comprehensive cognitive evaluation to rule out MCI according to the MDS Level II criteria⁷⁶ using the Repeatable Battery for the Assessment of Neuropsychological Status (RBANS)⁹³ and additional tests to assess frontal-executive functioning including the Stroop Test,⁹⁴ letter fluency (F-A-S),⁹⁵ and Trail Making Test parts A and B.⁹⁶ The tests will be scored immediately

to determine eligibility. Eligible subjects will be randomized to two groups: PD-MI and PD-Con. Brief description of the tests:

Weschler Test of Adult Reading: Is an assessment of intelligence that has participants pronounce 50 irregularly spelt words. The test typically takes 5-10 minutes to complete.

RBANS: Assesses 5 domains of cognition, 1) immediate memory, 2) Visuospatial/Constructional, 3) Language, 4) Attention, 5) Delayed Memory. Completion time is roughly 30 minutes.

Stroop test: Is a measure of attention that has the participant read through a list of words or naming colors as quickly as possible within 45 seconds.

F-A-S verbal fluency test: Measures verbal fluency by having the participant verbally produce as many words as possible that begin with the letters F, A, and S, within a one-minute timespan.

Trail Making Tests A & B: Consist of 25 circles spread over a sheet of paper, the subject is tasked with connecting each circle by following a specific pattern in a 5-minute timespan.

For all eligible subjects: We will administer the Neuro-QoL version 2 Cognitive Function survey to eligible subjects to assess self-reported cognitive functioning in everyday life.⁹⁷ We will administer the Modified Six-Elements Test.⁹⁸ The test consists of three tasks (simple arithmetic, written picture naming, dictation) each of which has two subtasks. The subject is required to attempt at least part of each of the six subtasks within 10 min, but without switching directly between subtasks within the same task category. The tests assess the ability to create and maintain goals and intentions, formulate a plan, organize behavior over time, and execute the plan at appropriate times.⁹⁹

For eligible subjects in the PD-MI group: We will perform a structured cognitive interview to determine the subject's cognitive difficulties during everyday tasks. Information gathered from this interview will help with personalized mental imagery guidance.

Visit 2: Baseline neuroimaging experiments: Visit 2 will be scheduled within two weeks following Visit 1. All subjects will complete the Questionnaire upon Mental Imagery (QMI) Vividness of Imagery Scale¹⁰⁰ for evaluation of baseline imagery skills. All subjects will then perform fMRI tasks in the scanner. The mental imagery tasks will always be performed before the video-watching tasks to avoid possible carryover effects from the videos.

Mental imagery tasks: All subjects will receive instructions on how to perform mental imagery of goal-oriented daily tasks and practice guided imagery first outside the scanner. Subjects will then perform mental imagery of four different goal-oriented tasks in the scanner. We will keep the goals constant across subjects, but will not prescribe the specific steps or events. After each imagery run in the scanner, subjects will give an account of their imagery content which will be recorded.

Video-watching tasks: All subjects will also watch videos of four different everyday tasks (e.g., grocery shopping, preparing a meal) in the scanner. After each video-watching run in the scanner, subjects will answer questions about the content of the videos.

Scanning procedures: We will conduct the MRI experiments in a Siemens Prisma 3.0 Tesla human research magnet with a 64-channel head coil in the MRRC. First, T1-weighted high-resolution MPRAGE anatomical images (voxel size: 1 x 1 x 1 mm) will be collected for an accurate localization of the fMRI data. Then, axial, T2*-weighted, echo planar functional images will be collected (voxel size: 3.5 x 3.5 x 4 mm, 36 slices, FoV: 224 mm, TR: 2000 ms, TE: 25 ms, flip angle: 90°). There will be four mental imagery and four video-watching runs each lasting 4 min 18 s. During the mental imagery tasks, subjects will keep their eyes closed at all times and receive auditory instructions. During the video-watching runs, subjects will keep their eyes open and receive visual instructions.

Training period

Mental Imagery Training: Subjects in the PD-MI group will receive personalized training during one-on-one sessions 3 times a week for the first 4 weeks. Training will be offered via Zoom. Subjects will be guided to mentally simulate the planning and implementation of everyday tasks (e.g., going grocery shopping). The training sessions will last about 15-20 min. We will also record the mental imagery scripts for self-practice on no-training days in the first 4 weeks and for daily homework practice in the subsequent 2-week block. After practice, subjects will be asked to submit a detailed daily mental imagery diary via the Yale REDCap online survey platform. We will structure this diary based on the key elements of mental imagery including the setting of the activity, components of the activity, contextual cues, episodic details, emotional experiences, and vividness and difficulty level of the mental imagery exercise. Subjects will also be called once a week in the last 2 weeks for check-in.

Psychoeducation: Subjects in the PD-Con group will receive psychoeducation 3 times a week for 4 weeks regarding cognitive functioning and brain health in PD. Subjects will receive private video links with pre-recorded PowerPoint lectures covering topics such as basic brain anatomy, neuroplasticity, attention-executive function, memory, speech-communication, hallucinations and delusions, sleep, diet, physical activity, mood disorders, stress, and social bonds. The lectures will last about 15-20 min and will be accompanied by three multiple-choice questions to be completed via REDCap online survey platform to assess content comprehension. On no-lecture days in the first 4 weeks and in the subsequent 2-week block, subjects will receive quizzes covering the lecture topics to be completed via REDCap online survey platform. Subjects will also be called once a week in the last 2 weeks for check-in.

Visit 3: Short-term outcome visit. Upon completion of the 6-week training, all subjects will return for repeat 1) mental imagery assessment using the QMI, 2) cognitive evaluation using a different form of the RBANS and the frontal-executive tests, 3) Neuro-QoL survey, 4) Modified Six-Element Test, and 5) fMRI scans while performing mental imagery and video-watching of the same goal-directed daily tasks as in Visit 2. We will use modified versions of the videos to minimize learning effects. After Visit 3, subjects in the PD-MI group will be encouraged to incorporate goal-directed mental imagery into their daily life. Subjects in the PD-Con group will be encouraged to retain the psychoeducational information.

Visit 4: Long-term outcome visit. This will be the final visit. Twelve weeks after Visit 3, all subjects will return for repeat cognitive and imaging evaluations. The same procedures as described in Visit 3 will be followed.

